**TABLE 1A: NCI CTCAE FOR NEUTROPENIA AND THROMBOCYTOPENIA‡**

Adverse Event	Grade				
	1	2	3	4	5
Neutrophils (ANC)	<LLN- $1.5 \times 10^9/L$	<1.5- $1.0 \times 10^9/L$	<1.0- $0.5 \times 10^9/L$	< $0.5 \times 10^9/L$	Death
Platelets	<LLN- $75 \times 10^9/L$	< $75-50 \times 10^9/L$	< $50-25 \times 10^9/L$	< $25 \times 10^9/L$	Death

‡ Units for blood cells counts are expressed as  $10^9/L$ , which is equivalent to  $10^3/\mu\text{l}$  or  $10^3/\text{mcl}$ . ANC = absolute neutrophil count.

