**TABLE 1B: INTERVENTIONS FOR NEUTROPENIA AND THROMBOCYTOPENIA BY NCI CTCAE GRADE**

Adverse Event	Grade				
	1	2	3	4	5
Neutrophils (ANC)	None	None	Interrupt pomalidomide treatment, follow CBC weekly Resume pomalidomide when ANC is $>1.0 \times 10^9/L$ , at 1 mg/day less than previous dose*	Interrupt pomalidomide treatment, proceed as for Grade 3	Off study
Platelets (thrombocytopenia)	None	None	Interrupt pomalidomide treatment, follow CBC weekly Resume pomalidomide when platelets are $>0.5 \times 10^9/L$ , at 1 mg/day less than previous dose	Off study drug permanently	Off study

\* For Grade 3 neutropenias in which the ANC is  $>0.8 \times 10^9/L$ , patient may remain on the same dose of drug for up to 1 week at which time a repeat CBC should be obtained. If the ANC is persistently less than  $1.0 \times 10^9/L$ , study drug should be discontinued until recovery of the ANC to  $>1.5 \times 10^9/L$  and the patient then restarted on the next lower dose.

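### Protocol Table 1B gives no usable dose step for a participant already on 2 mg, and lets Grade 4 neutropenia restart at a lower count than a persistent mild Grade 3

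*Protocol*

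**What the plan says.** Protocol Section 6.1.8.3 names haematologic toxicity as the drug's main toxicity and directs dose changes according to Tables 1A and 1B.

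- **Grade 3 neutropenia (table cell).** Hold drug and check the CBC weekly. "Resume pomalidomide when ANC is" above 1.0 × 10⁹/L, "at 1 mg/day less than previous dose".
- **Grade 4 neutropenia (table cell).** "Interrupt pomalidomide treatment, proceed as for Grade 3".
- **Footnote.** For Grade 3 with ANC above 0.8, the "patient may remain on the same dose of drug for up to 1 week at which time a repeat CBC should be obtained". If the count is persistently below 1.0, "study drug should be discontinued until recovery of the ANC to" above 1.5, with "the patient then restarted on the next lower dose".
- **Grade 2 neutropenia.** No action.
- **Grade 3 thrombocytopenia.** The same 1 mg/day step-down wording as for neutrophils.

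The dose ladder is set elsewhere. The Protocol Summary, Sections 6.1.2 and 6.1.7, and SAP Section 8.3 give 4 mg as the starting dose, with 3 mg and 2 mg as the only reductions. Section 6.1.6 forbids breaking or opening capsules.

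**The concern.** A re-exposure rule should be one that every site can follow, and it should not be easier on the worse event without a reason. Table 1B falls short on both counts.

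At 2 mg, the instruction points to a dose that does not exist. The protocol does say what happens when 2 mg fails for muscle cramping (Section 6.1.8.8), but not for the toxicity it calls primary.

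On restart, a participant whose ANC fell below 0.5 may resume at a count at which another participant, whose ANC sat at 0.9 through the optional week, is still held. What is at stake is consistent and cautious handling of neutropenia across sites in a non-malignant disease. Efficacy inference is not involved.

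**Working it through.** No sample size, power or alpha figure bears on this, so the check is to trace the rules.

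**Inputs**

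- Neutrophil grades (Table 1A, × 10⁹/L): Grade 2 is below 1.5 down to 1.0; Grade 3 is below 1.0 down to 0.5; Grade 4 is below 0.5.
- Restart rules: Table 1B cells and footnote.
- Doses: 4, 3 and 2 mg (Protocol Summary, 6.1.2, 6.1.7; SAP 8.3).

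**Restart threshold by path**

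| ANC at detection | What happens | Restart at ANC | Source |
|---|---|---|---|
| 0.4 (Grade 4) | held | > 1.0 | Grade 4 cell, via Grade 3 cell |
| 0.6 (Grade 3) | held | > 1.0 | Grade 3 cell |
| 0.9 (Grade 3) | held at once | > 1.0 | Grade 3 cell |
| 0.9 (Grade 3) | week on drug, repeat 0.9 | > 1.5 | footnote, explicit |
| 0.9 (Grade 3) | week on drug, repeat 0.6 | > 1.5 | footnote, likely reading but not spelled out |
| 0.9 (Grade 3) | week on drug, repeat 0.4 | > 1.5 | footnote, likely reading but not spelled out |

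Three paths restart at > 1.0, one explicitly at > 1.5, and two at > 1.5 by implication. The gap is 1.5 − 1.0 = 0.5 × 10⁹/L, the full Grade 2 band of Table 1A. At any count above 1.0 and up to 1.5, the 0.4 case in the first row may be back on drug while the 0.9 case in the fourth row is still held.

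The third and fourth rows start from the same count and differ only in whether the optional week was used. So the stricter bar follows the path taken, not the grade alone.

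**Dose step**

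- 4 − 1 = 3 mg: supplied.
- 3 − 1 = 2 mg: supplied.
- 2 − 1 = 1 mg: not supplied, not a permitted reduction, and not obtainable from a 2 mg capsule under Section 6.1.6.

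The 1 mg/day wording is in the Grade 3 cells for both neutrophils and platelets, and Grade 4 neutropenia inherits it by reference. The footnote's next-lower-dose wording is better, but it too has no meaning at 2 mg.

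**Comparator not used.** The platelet row is not offered as an example of correct ordering. As the text reads, its restart value is > 0.5 × 10⁹/L, far below the Grade 4 limit of 25 × 10⁹/L in Table 1A. That may be a misprint or an artefact of text extraction.

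**The case against.** The case for leaving the table alone has several sound parts.

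- **The bars differ by path.** The > 1.5 bar applies only when the optional week has been used and has failed. The revision history for version 2.6 shows that the week was a deliberate allowance, so a stricter condition after it may also be deliberate. Grade 4 must stop at once, whereas Grade 3 above 0.8 may continue at full dose for a week. A reader might infer that Table 1B systematically reverses caution by severity. The documents do not support that: in the table cells Grade 4 is handled the same as Grade 3, and the anomaly is confined to the restart count in the footnote.
- **Restart above 1.0 is coherent in itself.** Grade 2 neutropenia calls for no action, so a reduced-dose restart in that range fits the table. Nor does the Section 6.1.8.3 statement about a lower threshold than in myeloma settle the matter, because it concerns intervention and discontinuation, not restart. The documents therefore do not show that > 1.0 is unsafe.
- **The 2 mg gap probably fails safe.** No site can dispense 1 mg, so the likely outcome is a hold (Section 6.1.8.4) or a stop (Section 7.3.5). For neutropenia alone it takes a third qualifying episode to get there (4 to 3, 3 to 2, then again), although earlier reductions for other toxicities shorten that. A reader might infer excess exposure; nothing in the documents shows it.

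All of this limits the point but does not remove it. A condition attached to the optional week explains why the footnote is strict; it does not explain why Grade 4 gets less. Investigator discretion allows a longer hold or a stop, but sets no count and no rule at the bottom of the ladder.

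**Conclusion.** The point holds as two wording defects in a safety rule. The instruction for a participant on 2 mg cannot be followed. The restart thresholds are inconsistent across paths, with an unexplained gap of 0.5 × 10⁹/L that favours Grade 4 over a persistent 0.9.

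It is a minor correction. The documents give no frequency of Grade 3 or 4 neutropenia and none of participants reaching 2 mg, so the number affected cannot be stated, and the 0.5 measures a gap between rules, not harm. Alpha, power and the primary analysis are unaffected.

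The conclusion rests on reading the footnote as limited to its own opening condition (Grade 3, ANC above 0.8). A reader who applied > 1.5 to any persistent count below 1.0 would see less inconsistency, but the Grade 4 cell refers to the Grade 3 rule and a Grade 4 count does not meet that condition. If both readings are possible, sites may differ, and clarification is still needed.

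**What to change.** - **Dose step.** In both Grade 3 cells, replace the 1 mg/day step with the next lower supplied dose (4 to 3 to 2 mg), and permanently discontinue study drug if the toxicity recurs at 2 mg.
- **Restart count.** Use one ANC threshold for all Grade 3 and 4 neutropenia, or make Grade 4 at least as strict as the footnote. The sponsor's clinicians should confirm the value; the documents do not dictate it.
- **Footnote scope.** State that the footnote governs once the optional week is used, whatever the repeat count below 1.0.
- **While editing the table,** check the platelet restart value against the source.

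The cost is a few words in Table 1B and a site memo. Some participants would be held slightly longer.

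If dosing is over, as the SAP's record of masked review before database lock (Section 7.6) suggests it may be, the change helps no current participant and matters only for re-use of the protocol. An optional listing of ANC and dose level by visit, for participants with a lowest post-baseline neutrophil value below 1.00 K/uL, could then be drawn from data already captured (Protocol 7.2.1.1; SAP 8.3 and 9.2). It would be limited to study visits, because interim weekly CBCs and the rule each site applied may not be in the database.

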#### 6.1.8.4 DOSE DISCONTINUATION BASED ON INVESTIGATOR'S DISCRETION

Pomalidomide may be held for an indefinite period at the discretion of the investigator for reasons including but not limited to safety and/or patient benefit (for example, surgery or other drug or disease related or unrelated medical problem). Study drug can be resumed at the discretion of the investigator based on the investigator's opinion that it is safe to do so. Patients should still attend regular study visits while study drug is held.

If the study drug is held during a cycle, the patient may begin the next dose cycle even if the previous cycle was not completed, assuming that the reason for holding the drug was not due to an adverse event requiring dose adjustment.

#### 6.1.8.5 SURGERY

In the specific case of surgery it is recommended that pomalidomide be stopped at least 7 days prior to surgery. Pomalidomide may be restarted 14-21 days after surgery, at the investigator's discretion.

#### 6.1.8.6 FATIGUE

Fatigue may be observed in some patients. This may be difficult to separate from fatigue due to underlying HHT/anemia. For fatigue of CTCAE Grade 3 or higher ([https://ctep.cancer.gov/protocoldevelopment/electronic\\_applications/ctc.htm](https://ctep.cancer.gov/protocoldevelopment/electronic_applications/ctc.htm), version 4.0), pomalidomide may be stopped for 1-2 weeks at the investigator's discretion and then resumed at a dose of 3 mg daily, or simply reduced to a dose of 3 mg/daily. This dose may be continued for the remainder of the study or further reduced to 2 mg daily if fatigue is persistent.

#### 6.1.8.7 RASH

The incidence of rash in patients with myeloma treated with pomalidomide is < 10%, though in one study of myeloma patients only 1 of 70 patients were forced to stop drug because of rash. The rash usually develops at the time of drug initiation, and involves the trunk and extremities and may be intensely pruritic. It may sometimes resolve with continued therapy, and is often not of sufficient severity to require drug cessation. Recommended therapies include topical hydrocortisone, oral corticosteroids, antihistamines, cimetidine, oatmeal baths, and ketoconazole shampoo.

#### 6.1.8.8 MUSCLE CRAMPING

In the case of muscle cramping, which may occur in some patients on higher doses of pomalidomide, treatment with over-the-counter quinine water as well as muscle relaxants such as cyclobenzaprine is allowed. If these do not diminish the intensity of symptoms to a tolerable level, the dose of pomalidomide may be reduced to 3 mg/day for two weeks, and the effect on cramping assessed. If this is unsuccessful in improving symptoms, the dose may be reduced to 2 mg/day. If symptoms remain intolerable, the patient will be removed from the study.

#### 6.1.8.9 THROMBOEMBOLISM

Thromboembolic disease has been associated with pomalidomide in patients with multiple myeloma, who are often on concomitant high-dose corticosteroids and have a predisposition to thrombosis due to their underlying cancer. Thrombosis has not been observed in a pilot study of HHT treated with pomalidomide with approximately 60 pt-months of exposure. The development of thrombosis in a patient on this study being treated with pomalidomide warrants study drug discontinuation.

#### 6.1.8.10 HEPATOTOXICITY

Pomalidomide hepatotoxicity is rare. Elevations in bilirubin or transaminases > 3 times the baseline value should prompt temporary discontinuation of pomalidomide. Laboratory testing should be

performed two weeks after discontinuation to assure that abnormalities have resolved. If so, therapy may be resumed at a dose of 3 mg/day.

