### 5.2 PARTICIPANT EXCLUSION CRITERIA

1. Women currently breast feeding or pregnant
2. Renal insufficiency, serum creatinine  $> 2.0 \text{ mg/dl}$
3. Hepatic insufficiency, bilirubin  $> 2.0$  (or  $> 4.0$  in the setting of a prior clinical or genetic diagnosis of Gilbert's syndrome) or transaminases  $> 3.0 \times \text{normal}$
4. Prior treatment with thalidomide or other Immunomodulatory imide drugs (IMiDs) within previous 6 months
5. Prior treatment with bevacizumab (systemic or nasal) within previous 6 weeks\*

6. Prior treatment with pazopanib within previous 6 weeks\*
7. The use of octreotide or oral estrogens within the previous month\*
8. History of prior unprovoked thromboembolism confirmed by venous ultrasound or other imaging modalities
9. Known peripheral neuropathy, confirmed by neurologic consultation
10. Known underlying hypoproliferative anemia (i.e. myelodysplasia, aplastic anemia)
11. Currently enrolled in other interventional trials
12. Known hypersensitivity to thalidomide or lenalidomide
13. The development of erythema nodosum if characterized by a desquamating rash while taking thalidomide or similar drugs
14. Known *SMAD-4* mutation, unless there has been a colonoscopy with normal (negative) results, or in which the patient has had no more than 5 small (in the opinion of the gastroenterologist) colonic polyps completely removed within the preceding 18 months
15. Anything that in the investigator's opinion is likely to interfere with completion of the study

\* Use of these treatments is not permitted during study participation. See protocol section 7.6 for additional details regarding prohibited treatments.

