### 7.3.2 BASELINE/RANDOMIZATION

A period of at least 28 days after the screening visit will be required before the baseline/randomization visit, which must be conducted in-person. The baseline visit will be synonymous with the day of randomization and will include the following:

- Verification of inclusion/exclusion criteria
- Obtain ESS with 28-day recall
- Complete QOL instruments
- Perform pregnancy testing for women of child bearing potential
- Review of concomitant medications and adverse events
- Record vital signs, results of physical exam
- Collect laboratory samples for CBC, iron studies, and genetic testing
- Collect biorepository blood samples
- Collect epistaxis duration information
- Randomization and study drug order
- Study drug dispensation

Results from the laboratory assessments at baseline should not be used to re-establish eligibility criteria; study eligibility is determined by assessments completed at the screening visit.

If the screening visit was done in-person and study eligibility is confirmed, randomization and study drug order may be done 3-5 days before the baseline visit to ensure that study drug is available on site for dispensation on the day of visit. Patients may be instructed to initiate the drug the same day or the following day.

If the screening visit was done remotely, randomization and study drug order will be done at the baseline visit. A detailed physical examination will be performed at the baseline visit and biorepository sample collection tube will include PAXgene RNA tube in addition to the SST, sodium citrate and EDTA plasma tubes.

After randomization, study drug will be shipped overnight to the study site (or directly to the patient) from the experimental pharmacy. Patients will be instructed to initiate the drug upon receipt or the following day.

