4.2 Study Population

The study population is defined by the following eligibility criteria.

Inclusion Criteria:

1. A clinical diagnosis of HHT as defined by the Curacao criteria
2. Age > 18 years
3. Platelet count $\geq 100 \times 10^9/L$
4. WBC $\geq 2.5 \times 10^9/L$
5. INR ≤ 1.4 and normal ± 2 sec activated partial thromboplastin time (aPTT or PTT per local laboratory designation) by local laboratory criteria (except for patients on a stable dose of warfarin or direct oral anticoagulants)
6. Epistaxis severity score ≥ 3 measured over the preceding three months, measured at the screening visit
7. A requirement for anemia, as determined by local laboratory hemoglobin assessment and normal ranges, and/or parenteral infusion of at least 250 mg of iron or transfusion of 1 unit of blood over the 24 weeks preceding the screening visit
8. All study participants must agree to be registered into the FDA mandated POMALYST REMS® program, and be willing and able to comply with the requirements of the POMALYST REMS® program
9. Females of childbearing potential (FCBP) must adhere to the pregnancy testing schedule mandated by the POMALYST REMS® program.
10. Ability to understand and sign informed consent

Exclusion Criteria:

1. Women currently breast feeding or pregnant
2. Renal insufficiency, serum creatinine > 2.0 mg/dl
3. Hepatic insufficiency, bilirubin > 2.0 (or > 4.0 in the setting of a prior clinical or genetic diagnosis of Gilbert's syndrome) or transaminases $> 3.0 \times$ normal
4. Prior treatment with thalidomide or other Immunomodulatory imide drugs (IMiDs) within previous 6 months
5. Prior treatment with bevacizumab (systemic or nasal) within previous 6 weeks
6. Prior treatment with pazopanib within previous 6 weeks
7. The use of octreotide or oral estrogens within the previous month
8. History of prior unprovoked thromboembolism confirmed by venous ultrasound or other imaging modalities
9. Known peripheral neuropathy, confirmed by neurologic consultation
10. Known underlying hypoproliferative anemia (i.e., myelodysplasia, aplastic anemia)
11. Currently enrolled in other interventional trials
12. Known hypersensitivity to thalidomide or lenalidomide.
13. The development of erythema nodosum if characterized by a desquamating rash while taking thalidomide or similar drugs.
14. Known SMAD-4 mutation
15. Anything that in the investigator's opinion is likely to interfere with completion of the study

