10.4 Laboratory Evaluations

Laboratory exams (include blood chemistry and hematology) will be collected from each patient and will be summarized by study visit. Box and whisker plots will be generated to show the changes across study visits for key safety labs. These have been produced for the DSMB reports.

If applicable, linear mixed effect models will be constructed modeling change from baseline for key safety lab values over time with study time treated categorically and will be used to compare any post-baseline measures to baseline. Change from baseline will be assessed for substantial violations of normality and if so, a transformation will be considered.

Incidence of treatment-emergent abnormal safety labs at any post-baseline timepoint for all collected lab parameters will be tabulated (similar to that produced for the DSMB reports but DSMB was not focused on treatment-emergent labs), and treatment groups will be compared with chi-squared or Fisher's exact test, if applicable. Treatment-emergent abnormal is defined as a lab value post-baseline that is outside the normal range during the treatment period but is within the normal range at baseline (or at screening, if the baseline value is missing).

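### The liver hold rule is relative to baseline only, so a participant with ALT and AST both at the entry limit gets no transaminase-driven prompt until above 9 × normal

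*Protocol*

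**What the plan says.** Protocol 6.1.8.10 is the only liver-specific hold rule in either document: "Elevations in bilirubin or transaminases > 3 times the baseline value should prompt temporary discontinuation of pomalidomide". It names no multiple of normal, no bilirubin value and no CTCAE grade. Tests are repeated two weeks after stopping. If the abnormalities have resolved, dosing may restart at 3 mg/day, but resolution is not defined.

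The entry limits are in exclusion 3 (Protocol 5.2, repeated in SAP 4.2). The bilirubin part reads "Hepatic insufficiency, bilirubin > 2.0 (or > 4.0 in the setting of a prior clinical or genetic diagnosis" and goes on to name Gilbert's syndrome. The transaminase part excludes only values above 3.0 × normal. A value exactly at a limit is therefore eligible.

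On what counts as baseline, Protocol 7.3.2 says "The baseline visit will be synonymous with the day of randomization". The same section says "Results from the laboratory assessments at baseline should not be used to re-establish eligibility criteria". SAP 10.4, in defining treatment-emergent laboratory abnormalities, takes the baseline value, "or at screening, if the baseline value is missing".

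Other toxicities have grade-based rules. At Grade 3, Table 1B begins "Interrupt pomalidomide treatment, follow CBC weekly" for both neutrophils and platelets. Table 1D holds drug for Grade 2 neuropathy and stops it permanently at Grade 3.

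**The concern.** A purely relative trigger rises with the starting value. Followed as written, it acts soonest in participants with normal liver tests and latest in those who enter with raised ones. Protocol 2.3.1 lists hepatotoxicity among the known risks of the drug, and exclusion 3 deliberately lets in people with raised values, so the combination can arise.

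The stakes are patient safety and consistency of holds across up to 15 sites. Without a stated value, any earlier hold rests on each investigator's judgement.

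**Working it through.** The documents give no hold level in multiples of normal, so there is no planned figure to reproduce. The check is direct arithmetic.

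**Inputs**
- Trigger: above 3 × baseline (Protocol 6.1.8.10).
- Highest eligible values: transaminases 3.0 × normal; bilirubin 2.0, or 4.0 with Gilbert's (Protocol 5.2, SAP 4.2). The documents print no unit for bilirubin.
- Baseline: week 0, the natural reading of 7.3.2.

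**Present rule: prompt level = 3 × baseline**

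| Test | Baseline | Prompt above |
|---|---|---|
| Transaminase (× normal) | 1.0 | 3.0 |
| Transaminase | 1.5 | 4.5 |
| Transaminase | 2.0 | 6.0 |
| Transaminase | 2.5 | 7.5 |
| Transaminase | 3.0 (entry limit) | 9.0 |
| Bilirubin | 2.0 (entry limit) | 6.0 |
| Bilirubin, Gilbert's | 4.0 (entry limit) | 12.0 |

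**Conditions on the 9 × figure**
- Both enzymes must start at the limit. With an assumed ALT of 3.0 and AST of 1.2, AST prompts at 3 × 1.2 = 3.6 × normal, well before ALT reaches 9.0.
- Bilirubin must not triple first, since that also triggers the hold.
- Nine is not a ceiling. Week 0 results cannot undo eligibility, so the week 0 value may exceed 3.0. An assumed week 0 value of 4.0 gives 3 × 4.0 = 12.0 × normal.

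**Effect of adding an absolute limit C**

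The prompt becomes the smaller of 3 × baseline and C. C matters only when baseline is above C/3. The documents do not print the hepatic Grade 3 values, so C is assumed over a range.

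| Test | Assumed C | Changes the rule for baseline above | Prompt at the entry limit | Lowered by |
|---|---|---|---|---|
| Transaminase (× normal) | 4 | 4/3 = 1.33 | 9.0 to 4.0 | 5.0 |
| Transaminase | 8 | 8/3 = 2.67 | 9.0 to 8.0 | 1.0 |
| Bilirubin, no Gilbert's | 3.0 | 3.0/3 = 1.0 | 6.0 to 3.0 | 3.0 |
| Bilirubin, no Gilbert's | 5.0 | 5.0/3 = 1.67 | 6.0 to 5.0 | 1.0 |

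At a transaminase baseline of 1.0 × normal or below, the present rule already acts at or below 3.0 × normal, and nothing changes anywhere in this range.

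**What else could prompt an earlier hold**

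The metabolic panel is drawn at screening, at the start of therapy and monthly (Protocol 7.2.1.1 and Table 4). Having results at the visit is strongly recommended (7.3.3). All adverse events are recorded (8.3) and go to the independent medical monitor (10.4.7.1). Investigators may reduce the dose (6.1.7) or hold drug (6.1.8.4). These provisions detect a rise or permit action, but none gives a liver value at which to act. The halting rule in 8.5 counts only thromboembolic events.

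**The case against.** The best case for the plan is that a baseline-relative rule is a reasonable choice here. The trial admits people with raised liver tests, including those with Gilbert's, in a disease that can involve liver AVMs. An absolute limit may stop drug for pre-existing disease. The protocol calls hepatotoxicity rare, and the drug-related events it reports from its small pilot include no hepatic event. The 9 × case needs both enzymes at the entry limit, and the documents do not say how many participants enter with raised values. All of this stands. It limits the weight of the point but supplies no missing value.

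The comparison with other toxicities also needs care. A reader might infer that the liver is the one exception to a uniform Grade 3 hold policy, and that is not so. "For fatigue of CTCAE Grade 3 or higher" the action is at the investigator's discretion. Rash and muscle cramping have no grade-based hold, and the renal rule is itself relative to baseline. The firm contrast is only with the cytopenias (Table 1B) and neuropathy (Table 1D).

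An absolute limit carries its own risk. If resolution stays undefined, a participant with chronic elevation might never qualify to restart. Under 7.3.5, permanent discontinuation leads to the current cycle visit and an end-of-study visit four weeks later, so the week 24 measurement can be lost. This is a fair objection, and the fix has to deal with it.

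**Conclusion.** The point holds as a low-cost safety improvement. The only stated liver prompt is 3 × baseline. With ALT and AST both at the entry limit, it is silent on transaminases until above 9 × normal, and for bilirubin from 2.0 until above 6.0. These figures assume that week 0 equals the entry limit. How much an absolute limit would gain at that limit depends on the Grade 3 values: 1.0 to 5.0 × normal over the assumed transaminase range.

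Three stronger readings are not supported:
- A reader might infer that drug must continue up to 9 × normal. Section 6.1.8.4 allows an earlier hold, and 6.1.8.10 does not forbid one.
- A reader might infer that hepatic events would be missed or misgraded. Recording, CTCAE grading and tabulation do not depend on this rule.
- SAP 9.2 lists raised alanine aminotransferase among the possibly related events of at least moderate severity that masked review judged medically relevant. A reader might take this as evidence that the rule failed. The entry gives no arm, value or baseline, so it shows only that such events were captured.

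**What to change.** In Protocol 6.1.8.10:

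1. Keep the 3 × baseline trigger and add a second one: a post-baseline ALT, AST or total bilirubin of CTCAE v4.0 Grade 3 or higher also prompts a temporary hold, whichever comes first.
2. Exempt participants admitted under the Gilbert's allowance from the bilirubin part of the new trigger. For them the 3 × baseline rule for bilirubin stays (above 12.0 from 4.0), and the ALT and AST parts still apply.
3. Define the baseline value as the week 0 result, or the screening result if week 0 is missing, in line with SAP 10.4.
4. Define resolution as return to the participant's baseline value or to Grade 1 or lower, so that chronic elevation does not make the hold permanent.

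The two-week retest and the 3 mg/day restart stay as they are.

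The cost is wording only. The panels are already drawn, and CTCAE v4.0 is already the grading scale (8.2.1). The downside is a few more temporary holds and restarts at 3 mg/day among participants entering with raised values, with a small remaining risk of permanent discontinuation and loss of the week 24 visit under 7.3.5. A participant already at Grade 3 at week 0 would meet the new trigger at the next panel if nothing changed. The SAP already reports masked review before database lock (7.6), so the change would serve anyone still on drug and any later use of these dosing rules.
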